6.8 Subject Withdrawal

Subjects must be informed about their right to withdraw from the clinical study at any time and for any reason without sanction, penalty or loss of benefits to which the subject is otherwise entitled. Withdrawal from the clinical study will not jeopardize their future medical care or relationship with the investigator. Subjects will be requested to specify the reason for the request to withdraw. The investigator must make all reasonable efforts to retain the subject in the clinical study until completion of the clinical study.

A subject will be considered 'Lost to Follow-up' after one missed visit and a minimum of two unsuccessful phone calls from study site personnel to the subject or subject's contact to schedule the next follow-up visit. These two phone calls must be documented in the subject's hospital records. If the subject is deemed lost to follow-up, a letter should be sent to the subject's last known address or to the subject's general practitioner (GP) and a copy of the letter must be maintained in the subject's hospital records.

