7.1 Endpoints

The endpoints for evaluating the objectives are as following:

- Summary of subjects that used EnSite™ AutoMap and AutoMark module
- Summary of EnSite™ Automap and AutoMark module software settings used per arrhythmia
- Assessment of EnSite™ AutoMap Module including:
 - o Mapping time associated with (re-)mapping one or multiple arrhythmias per catheter type used in a single subject
 - o Used Points per Minute per catheter type stratified by arrhythmia type and mapping type
- Rate of acute success based on pre-defined procedural endpoints
- Freedom from arrhythmia recurrence through 12 months
- Number of repeat ablations up to 12 months
- Summary of NavX patch placement locations used
- Number of gaps in lesions identified requiring touch-up ablation
- Changes in EQ-5D quality of life score at 6 and 12 months
- Number of unscheduled visits and hospitalizations due to arrhythmia
- Overall procedure time

- Overall system stability

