7.1.1 Analysis Methodology

The endpoints will be summarized descriptively based on available data or measurements in the analysis population. No hypothesis testing will be performed.

Summary of subjects that used EnSite™ AutoMap and AutoMark module:

- Overall usage of EnSite™ AutoMap Module:
This will be summarized by the number and proportion of subjects with a procedure that use EnSite™ AutoMap.
- Overall usage of AutoMark module:
This will be summarized by the number and proportion of subjects with a procedure that use AutoMark.

Summary of EnSite™ Automap and AutoMark Module software settings used per arrhythmia:

- Usage of EnSite™ AutoMap Module features:
Among the subjects with EnSite™ AutoMap module features used during the procedure, the initial settings of EnSite™ AutoMap features listed below will be summarized descriptively by each arrhythmia, as number and proportion or mean and standard deviation as appropriate.

AutoMap Settings:

- Score Threshold (%)
- Cycle length tolerance (ms)
- Speed limit (mm/s)
- Distance threshold (mm)
- Signal-to-Noise ratio (number)
- Force lower limit (grams)
- Force upper limit (grams)
- Enhanced Noise rejection enabled? (Y/N)
- Independent Scoring Interval enabled? (Y/N)

- Usage of AutoMark Module features:

Among the subjects with AutoMark features used during the procedure, the AutoMark features listed below will be summarized descriptively as number and proportion or mean and standard deviation as appropriate.

AutoMark Parameters (values and diameters of Lesion Color and Lesion Size Metrics):

- Energy (Joules)
- Time (Seconds)
- Impedance Drop (Ohms)
- Impedance Drop (%)
- Average Power (Watts)
- Maximum Power (Watts)
- Average Temperature (Degrees Celsius)
- Max. Temperature (Degrees Celsius)
- Average Force (Grams)
- Max. Force (Grams)
- *LSI (number) → OUS only*
- *FTI (gr/s) → OUS only*

AutoMark placement settings:

- AutoMark Spacing (mm)
- Min AutoMark Time (s)
- Away Time (s)

Mapping time associated with (re-)mapping one or multiple arrhythmias per catheter type used in a single subject:

- Mapping time will be summarized (e.g. as mean, median, standard deviation, minimum and maximum) across arrhythmia types and for each type of arrhythmia per catheter, as appropriate for the following map types:
 - o Manual
 - o AutoMap
 - o Combination Manual Map / AutoMap
 - o TurboMap™

Used Points per Minute per catheter type stratified by arrhythmia type and mapping type:

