- Mapping points per minute used will be summarized (e.g. as mean, median, standard deviation, minimum and/or maximum) across arrhythmia types and for each type of arrhythmia per catheter as appropriate, with following map types:
 - o Manual mapping
 - o AutoMap
 - o Combination Manual Map / AutoMap
 - o TurboMap™

Rate of acute success based on pre-defined procedural endpoints (refer to Appendix C):

- The number and proportion of subjects with acute success will be summarized.

Freedom from arrhythmia recurrence: Arrhythmia recurrence is defined as documented atrial arrhythmia for 30 seconds or longer or documented ventricular arrhythmia either treated by ICD or lasting 20 seconds or longer throughout the follow-up period.

- This analysis will be performed using the Kaplan-Meier (KM) analyses. The start date is the date of the index procedure. For subjects who do not experience an event, their follow up duration will be defined from the start date to the date of death, withdrawal, or last follow-up, whichever occurred later.
- Time to arrhythmia recurrence is defined as time from index procedure to the date of the first recurrence. For subjects with AF, events occurring within the blanking period (defined as the first 90 days after the index procedure) will be excluded from the analysis.

Number of repeat ablations up to 12 months. This will be summarized as:

- Total count of repeat ablations up to 12 months among all subjects in the analysis population defined in section 7.1.3
- Total number of subjects who experience at least one repeat ablation up to 12 months among all subjects in analysis population defined in section 7.1.3

Summary of NavX Patch placement locations used

- The number and proportion of subjects with NavX patches (Surface Electrode Patches) placed by location

Number of gaps in lesions identified during the procedure that require touch-up ablation:

- The number and proportion of subjects with gaps in lesions identified will be summarized and reported.
- The summary of number of gaps identified will be reported.
- The number and proportion of subjects where the AutoMark Module assisted in identifying these gaps will be summarized and reported.

Changes in EQ-5D quality of life score at 6 and 12 months:

- Changes in EQ-5D at 6 months from baseline, and changes in EQ-5D score at 12 months from baseline will be summarized.

Number of unscheduled visits and hospitalizations due to arrhythmia:

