7.1.2 Sample Size Determination

7.1.3 Analysis Populations

7.1.4 Subgroup Analysis

There are no pre-specified subgroup analysis for this clinical study.

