7.1.5 Missing Data

All data available for the endpoints specified among the analysis population will be used. Missing data will not be imputed.

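### Repeat ablations up to 12 months are reported only as raw totals with no allowance for follow-up time, so they understate repeat ablation if read as a 12-month risk

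*Combined protocol and SAP*

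**What the plan says.** Section 7.1 lists "Number of repeat ablations up to 12 months" among the endpoints. Section 7.1.1 gives it two summaries. The first is an overall tally of repeat procedures, taken over everyone in the section 7.1.3 population. The second counts people instead of procedures: "Total number of subjects who experience at least one repeat ablation up to 12 months among all subjects in analysis population".

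For this endpoint the section names no censoring rule, person-time rate, cumulative incidence or denominator of subjects followed to 12 months. For freedom from recurrence the same section says: "This analysis will be performed using the Kaplan-Meier (KM) analyses". It then defines how long event-free subjects are followed.

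The general rules are descriptive. Section 7.1.1 opens with "The endpoints will be summarized descriptively based on available data or measurements in the analysis population" and excludes hypothesis testing. Section 7.1.5 adds "Missing data will not be imputed".

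Follow-up can be incomplete in several ways. Section 6.8 allows withdrawal at any time, and classes a subject as lost "after one missed visit and a minimum of two unsuccessful phone calls from study site personnel". Section 9.2.1 records deaths on the Withdrawal form. Section 7.4 lets the sponsor run analyses before the 12-month follow-up is complete.

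The population is the one under the heading "7.1.3 Analysis Populations", whose text does not appear in the public copy. That absence is not a fault in the plan.

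**The concern.** The endpoint covers a fixed 12-month window, but the summaries do not record how much of that window each subject was observed for. A subject who leaves without a repeat ablation stays among all subjects and cannot contribute a later event. Repeat ablations after withdrawal or loss go unseen, so the observed total cannot exceed the true 12-month total in the same subjects, whatever the reason for leaving. The direction of the error is therefore known and only its size is uncertain.

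The third objective (section 5.2) is to relate system usage to patient outcomes, and section 7.2 says the results may feed best-practice recommendations. In a study without hypothesis tests the descriptive figures are the result. A reader will naturally divide the number re-ablated by the number of subjects and call the quotient a 12-month risk. That risk would look better than it is, and more so where retention is poorer.

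**Working it through.** The plan states no figure to reproduce. The readable text gives no sample size, repeat-ablation rate or dropout rate, so all values of p and d below are assumptions.

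**Inputs.** p is the true 12-month risk of a first repeat ablation. d is the share of subjects who leave before 12 months for reasons unrelated to repeat ablation. The hazard is constant, L = -ln(1-p) per year, and there are no deaths.

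**Crude proportion over all subjects** = (1-d)p + d·m, where m is the chance that a leaver was re-ablated, and so counted, before leaving.

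- Exit spread evenly over the year: m = 1 - (1-exp(-L))/L.
- Exit at 1 month, which the one-missed-visit rule in section 6.8 makes possible: m = 1 - exp(-L/12).

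For p = 10%, L = 0.1054, so m = 0.0509 (even exit) or 0.0087 (exit at 1 month). For p = 20%, L = 0.2231, so m = 0.1037 or 0.0184.

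| True p | d | Even exit | Exit at 1 month |
|---|---|---|---|
| 10% | 10% | 0.090 + 0.0051 = 9.5% | 0.090 + 0.0009 = 9.1% |
| 10% | 20% | 0.080 + 0.0102 = 9.0% | 0.080 + 0.0017 = 8.2% |
| 20% | 10% | 0.180 + 0.0104 = 19.0% | 0.180 + 0.0018 = 18.2% |
| 20% | 20% | 0.160 + 0.0207 = 18.1% | 0.160 + 0.0037 = 16.4% |

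The relative understatement is about 5% (d = 10%) to 10% (d = 20%) with even exit, and about 9% to 18% with exit at 1 month. With even exit, for p from 5% to 30%, it is about 2.5% at d = 5% and 14-15% at d = 30%. Exponential dropout gives nearly the same results.

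**Simulation check.** With 400,000 subjects, p = 15%, d = 20% and even exit, the crude proportion was 13.6% and one minus the Kaplan-Meier estimate was 15.0%. Among leavers, 7.8% had been re-ablated before leaving and were counted. With no deaths simulated, one minus Kaplan-Meier equals the cumulative incidence.

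**Early data cut (section 7.4).** If half the subjects have only 6 months of follow-up and p = 20%, the crude figure is 0.5 × 20% + 0.5 × (1 - 0.8^0.5) = 10.0% + 5.3% = 15.3%, about 24% low in relative terms.

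**The case against.** Four objections carry weight.

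1. *The plan names totals, not a proportion.* Nearby endpoints such as acute success and patch location ask for number and proportion; this one does not. A total of observed events is correct as a total. This stands: the error enters when the total is read as a 12-month risk. But an endpoint with a 12-month limit, counted over a stated population, invites that reading, and the plan offers nothing better.

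2. *The population is not visible.* If section 7.1.3 required complete follow-up, the point would fall. This stands as a condition. The readable text leans the other way: the recurrence analysis has a rule for subjects who die, withdraw or end follow-up without an event, which would have little purpose if early leavers were excluded. The section heading is plural, so a separate population cannot be ruled out.

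3. *Death is not lost information.* A subject who dies without a repeat ablation truly had none, so the count is right for that subject. This stands. Plain Kaplan-Meier with deaths censored would overstate the 12-month probability.

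4. *The size is unknown and may be small.* This also stands. With even exit the assumed loss is 0.5-1.0 points on a true 10% and 1.0-1.9 points on a true 20%. Having every dropout leave at 1 month is an extreme case.

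Two stronger readings are tempting. A reader might infer that everyone who leaves early counts as never re-ablated. The documents do not say so: a repeat ablation before exit is counted. That reading sets m to zero and would double the understatement at even exit, to 10-20%. A reader might also infer that planned comparisons between arrhythmia types or usage patterns are distorted. Section 7.1.4 pre-specifies no subgroup analysis and section 7.1.1 does not stratify repeat ablation, so this is a risk for later use of the figures only.

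**Conclusion.** The point holds in a limited form. The two totals ignore follow-up time, and read as a 12-month risk they can only be too low. At 10-20% dropout spread evenly over the year, the understatement is about 5-10% in relative terms. It is larger if subjects leave early or the data are cut before all reach 12 months, and negligible if few leave.

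The sizes rest on an assumed constant hazard, uninformative dropout and no deaths; the direction does not. The conclusion is conditional on section 7.1.3 not restricting the population to complete follow-up. No test or success decision depends on it. What is affected is how a descriptive figure will be understood, and its consistency with the method already chosen for recurrence.

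**What to change.** In section 7.1.1, keep both counts and add:

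- the cumulative incidence of first repeat ablation at 12 months, timed from the index procedure, with death as a competing event and censoring at withdrawal or last contact;
- total repeat ablations per 100 subject-years of follow-up;
- the number of subjects with complete 12-month follow-up.

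The cumulative incidence should carry the interpretation, because a rate per subject-year averages over follow-up and depends on its length if the hazard changes with time. Both additions still assume that leaving is unrelated to the need for another ablation, and the report should say so.

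This is a cheap improvement: about one sentence of analysis text. Exit dates are already needed for the recurrence analysis. Repeat-ablation dates are implied by the 12-month limit, but section 6.3.3 and Table 3 do not name them and the case report forms are held separately. The sponsor should confirm that they are captured, for example on the Health Care Utilization form. The only other cost is that the reported figure may be slightly less favourable.

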7.1.2 Sample Size Determination

7.1.3 Analysis Populations

7.1.4 Subgroup Analysis

There are no pre-specified subgroup analysis for this clinical study.

7.1.5 Missing Data

All data available for the endpoints specified among the analysis population will be used. Missing data will not be imputed.

7.2 Justification of Clinical Study Design

[figure not shown]
The EnSite Precision™ Cardiac Mapping System is a newly developed system that introduces features such as DE-MRI image integration, lesion marking automaticity, automatic mapping, and workflow flexibility to aid in the success of complex ablation procedures. Utilization of this system in the treatment of complex ablation procedures and its impact on patient outcomes is not well characterized. This clinical study is designed to collect a broad range of usage scenarios, therefore this clinical study has limited patient selection criteria and data collection is focused on EnSite Precision™ Cardiac Mapping System usage and patient outcomes.

The data collected from the procedure (performed per IFU and per standard practice of the physician) as well as the 12 month follow up period enables the Sponsor to review the system's standard practice

usage. This information will be added to the current knowledge and understanding of treatment options for patients with arrhythmias, which can assist the Sponsor to provide future recommendations for best practices to improve patient outcomes.

7.3 Overall Sample Size

7.4 Timing of Analysis

Data analyses will be performed at the completion of the 12-month follow-up period or as desired by Sponsor.

In addition, study progress and data may be summarized and reported as needed.

7.5 Success Criteria

7.6 Interim Analysis

7.7 Statistical Criteria for Termination

There are no statistical criteria for termination of this clinical study.

7.8 Deviations from Statistical Plan

If any deviations from the original statistical plan occur, such deviations will be documented in the clinical study report or statistical report containing the analysis results.

8 Risks and Benefits

The risks associated with the EnSite Precision™ Cardiac Mapping System can be found in the Instructions for Use. The clinical study does not require any additional procedures or assessments over the standard of care. There are no additional risks introduced to subjects due to participation in this study.

8.1 Risks Associated with the Clinical Study Device

8.1.1 Anticipated Adverse Device Effects

Refer to applicable IFU for list of Anticipated Adverse Device Effects.

8.1.2 Risks Associated with Clinical Study Assessments

Risks to subjects enrolled in this clinical study include those risks currently associated with other commercially available electrophysiology diagnostic procedures and RF catheter ablation procedures. The risks of the procedure are related primarily to mechanical injury to the heart and vessels from catheter manipulation and thermal injury due to RF current delivery, including the risk of thromboembolism and myocardial perforation, especially for ablations in the left atrium.

For those procedures where the physician applies sedation or anesthesia, the standard risks of anesthesia also exist and include allergic reactions, pneumonia, aspiration pneumonitis, atelectasis, prolonged sedation, other medical complications and in very rare cases, death.

8.2 Risk Control Measures

Every possible effort will be taken to minimize the risks, including:

- Careful selection of experienced Investigators for the study
- Training of Investigators/study nurses on the CIP
- Conducting the clinical study in accordance with the CIP, all applicable laws and regulations and any conditions of approval imposed by the appropriate IRB/EC or applicable regulatory authorities where the clinical study is performed
- Conducting the ablation procedures in accordance with the IFU of corresponding devices

8.3 Possible interactions with concomitant treatments

There are no interactions with concomitant medical treatments and/or concurrent medical interventions compared to standard practice.

8.4 Anticipated Benefits

The aim of this clinical study is to collect information on the use and the performance of the EnSite Precision™ Cardiac Mapping System.

The information collected in this clinical study will be added to the current knowledge and understanding of treatment options for patients with arrhythmias. Subjects participating in this clinical study are not expected to experience any additional benefit or harm compared to patients who are not participating in this clinical study as the clinical study will follow local standard practice.

8.5 Risk-to-Benefit Rationale

Catheter ablation is a recognized safe and effective treatment of cardiac arrhythmias. The EnSite Precision™ Cardiac Mapping System is believed to not introduce any unanticipated risks compared to current practice

8.6 History of Device Modifications or Recall

There have been no modifications or recalls in relation to safety and clinical performance of the EnSite Precision™ Cardiac Mapping System.

9 Requirements for Investigator Records and Reports

9.1 Deviations from CIP

A deviation is defined as an instance(s) of failure to follow, intentionally or unintentionally, the requirements of the CIP. The investigator should not deviate from the CIP.

In some cases, failure to comply with the CIP may be considered failure to protect the rights, safety and well-being of subjects; such non-compliance exposes subjects to unreasonable risks, e.g. failure to adhere to the inclusion/exclusion criteria. Investigators should seek to minimize such risks by adhering to the CIP.

The PI must maintain accurate, complete, and current records, including documents showing the date of and reason for each deviation from the CIP. Relevant information for each deviation will be documented as soon as possible on the applicable CRF. The site will submit the CRF to the Sponsor.

The PI is required to adhere to local regulatory requirements for reporting deviations to IRB/EC.

9.2 Safety Reporting

The devices used in this clinical study are market released and should be used according to IFU. As there are no safety driven endpoints, adverse events will not be collected during this clinical study. Complaints will be managed via the sponsor's standard Postmarket Surveillance process.

9.2.1 Subject Death

Subject deaths shall be reported to the IRB/EC as per local regulations and shall be reported on a Withdrawal form.

9.2.2 Complaints

The investigator will be responsible for reporting all complaints they became aware of during the study. A complaint is defined as any written, electronic or oral communication that alleges deficiencies related to the identity, quality, durability, reliability, safety, effectiveness or performance of a device after it is released for distribution.

The investigator must notify the Post Market Surveillance Department by submitting the information on the device via email to [REDACTED] as soon as possible after becoming aware of the complaint. This information will not be collected on a CRF for the study.

9.3 Source Records

Source documents will be created and maintained by the investigational site team throughout the clinical study. The data reported on the CRFs will be derived from, and be consistent with, these source documents, and any discrepancies will be explained in writing.

To facilitate data collection during the EP procedure, worksheets may be provided to the site where source data can be collected.

9.4 Records Retention

The Sponsor and the Principal Investigators will maintain the clinical study documents as required. Measures will be taken to prevent accidental or premature destruction of these documents. The Principal Investigator or the Sponsor may transfer custody of records to another person/party and document the transfer at the investigational site or the Sponsor's facility, as appropriate.

These documents must be retained by the investigational site for a period of 2 years (or longer if required by local regulations) after the conclusion of the clinical study and made available for monitoring or auditing by the Sponsor's representative or representatives of the applicable regulatory agencies.

All original source documents must be stored for the maximum time required by the regulations at the hospital, research institute, or practice in question. If original source documents can no longer be maintained at the site, the investigator will notify the Sponsor.

10 Clinical Data Handling

The Sponsor will be responsible for the data handling. The Sponsor and/or its affiliates will be responsible for compiling and submitting all required reports to governmental agencies. Data will be analyzed by the Sponsor and may be transferred to the Sponsor's locations worldwide and/or any other worldwide regulatory authority in support of a market-approval application.

